10.2.3 Pharmacokinetic Assessments

Blood samples for the determination of plasma diclofenac concentrations will be collected at specified visits after the application of the study drug as per the Schedule of Events in **Section 17.1**. A volume of approximately 4 mL of blood will be collected at Visit 4 (Day 14) and Visit 5 (Day 28); or at the Early Termination Visit, if applicable. The LC/MS/MS validation method will be used to analyze the plasma sample to determine the diclofenac concentrations and blood sampling times will be recorded.

The total blood volume collected will be approximately 40 mL (inclusive of pharmacokinetic and clinical safety laboratory collections).

11. ADVERSE EVENTS

11.1. Definitions

11.1.1 Adverse Events

An AE is defined as any untoward medical occurrence in a clinical investigation subject administered a pharmaceutical product that does not necessarily have a causal relationship with the product. An AE can therefore be any unfavorable and unintended sign (including a new, clinically important abnormal laboratory finding), symptom, or disease, temporally associated with the product, whether or not related to the product.

Pre-existing diseases or conditions will NOT be considered AEs unless there is an increase in the frequency or severity, or a change in the quality, of the disease or condition during the Double-blind Treatment Phase (Worsening of a pre-existing condition is considered an AE.).

Events occurring in subjects treated with placebo will also be considered AEs. However, AEs reported during treatment-free periods before study drug has been administered are not considered AEs; these events are captured on the eCRF as updates to the subject's medical history.

- All AEs encountered during the clinical study will be reported on the eCRF. All AEs, regardless of relationship to study drug or procedure, should be collected beginning from after the start of the study drug. AEs in clinical investigation subjects include any change in the subject's condition. This includes symptoms, physical findings, or clinical syndromes.
- An abnormal laboratory value may be considered an AE if the identified laboratory abnormality leads to any type of intervention whether prescribed in the protocol or not. It is up to the investigator to determine whether an abnormal laboratory value constitutes an AE. If an abnormal laboratory value is caused by a disease process, the disease process and not the laboratory abnormality should be listed as the AE (e.g., if new onset viral hepatitis is causing elevated ALT, hepatitis and not the elevated ALT should be listed as the AE).
- Examples of laboratory abnormalities, which should be considered as AEs include those which result in withdrawal of the study treatment, withholding study treatment pending some investigational outcome, reduction of dose of the study treatment, or additional concomitant treatment. All laboratory abnormalities considered to constitute an AE

should be reported on the appropriate AE page of the eCRF. Laboratory abnormalities do not need to be listed as separate AEs if they are considered to be part of a clinical syndrome that is being reported as an AE. It is the responsibility of the investigator to review all laboratory findings in all subjects. Abnormal values should be commented upon as to clinical relevance or importance on the eCRF or the laboratory report as appropriate. Medical and scientific judgment should be exercised in deciding whether an isolated laboratory abnormality should be classified as an AE.

- Every effort must be made by the investigator to categorize each AE according to its severity and its relationship to the study treatment.

11.1.2 Unexpected Adverse Event

An expected AE is one for which the nature or severity is consistent with the known AE profile of the product. For a study drug, the known information is contained in the IB which includes the HP-5000 Developmental Core Safety Information.

An unexpected adverse event is one for which the specificity or severity is not consistent with the current IB and Developmental Core Safety Information.

Furthermore, reports that add significant information on specificity or severity of a known, already documented adverse reaction constitute unexpected events.

11.1.3 Serious Adverse Events

A serious adverse event (SAE) is any untoward medical occurrence that at any dose:

- results in death
- is life-threatening.

NOTE: The term “life-threatening” in the definition of “serious” refers to an event in which the subject was at risk of death at the time of the event; it does not refer to an event which hypothetically might have caused death if it were more severe.

- Requires inpatient hospitalization or prolongation of existing hospitalization.

NOTE: An elective hospital admission to treat a condition present before exposure to the test drug, or a hospital admission for a diagnostic evaluation of an AE, does NOT qualify the condition or event as an SAE.

- Results in persistent or significant disability/incapacity.
- Is a congenital anomaly.

NOTE: A congenital anomaly in an infant born to a mother who was exposed to study drug during pregnancy is an SAE. However, a newly diagnosed pregnancy in a subject that has

received a study drug is NOT considered an SAE unless it is suspected that study drug interacted with a contraceptive method and led to the pregnancy.

- is an important medical event

NOTE: *Medical and scientific judgment should be exercised in deciding whether it is appropriate to consider other situations serious, such as important medical events that may not be immediately life-threatening or result in death or hospitalization but may jeopardize the subject or may require intervention to prevent one of the other outcomes listed in the definition above. Examples of such events are intensive treatment in an emergency room or at home for allergic bronchospasm, blood dyscrasias, or convulsions that do not result in hospitalization, development of drug dependency, or drug abuse.*

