8.2.2 Exclusion Criteria

A subject will be excluded from the study if the he or she meets any of the following criteria:

1. Body mass index (BMI) > 40.
2. The non-target knee pain severity score is [REDACTED] at Screening and Baseline (Day 0).
3. Any subject who disobeyed the restriction of prohibited therapies (i.e., use rescue medication) during Screening prior to the start of the Washout Period and 2 days prior to the Baseline Visit (V2).
4. Secondary OA of the knee (rheumatoid arthritis, gout, psoriasis, syphilitic neuropathy, ochronosis, metabolic or other primary bone disease or acute trauma).

5. Clinically significant elevation of serum creatinine (176.8 μ mol/L), aspartate aminotransferase (AST) or alanine aminotransferase (ALT) (3 x upper limit of normal [ULN]) at the Screening Visit.
6. Known allergy or hypersensitivity to the use of diclofenac, [REDACTED] [REDACTED] [REDACTED] [REDACTED] ethanol, acetylsalicylic acid (aspirin [ASA]), or any other NSAID..
7. Severe uncontrolled cardiac, renal, hepatic or other systemic disease.
8. A documented gastroduodenal ulcer (upper GI series or endoscopy) or any GI bleeding (except hemorrhoidal) within 6 months prior to Screening Visit.
9. Documented history of alcohol or drug abuse within 1 year prior to study entry or positive alcohol/drug screen findings at Screening or Baseline.
10. Presence of chondrocalcinosis on X-ray if associated with a history of pseudogout or inflammatory flare-ups.
11. MAJOR SURGERY: Previous damage or surgery to the target knee at any time (i.e., damage/reconstruction of the anterior or posterior cruciate ligaments).
12. MINOR SURGERY on the target knee defined as anything other than major surgery (as defined above) within 1 year before study enrollment.
13. Treatment with oral or intra-muscular corticosteroids within 90 days of Screening Visit, treatment of the target knee with topical or intra-articular corticosteroids within 90 days of Screening Visit, or topical or intra-articular corticosteroid treatment of any other joint within 30 days of Screening (see **Section 9.10.2**).
14. Any subject who had received intra-articular viscosupplementation (e.g., Synvisc[®]) in the target knee 90 days prior to Screening Visit.
15. Any subject who had used opioids 7 days prior to the Screening Visit.
16. Any subject who had previous exposure to HP-5000.

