11.2.5 Follow-up

ALL ongoing SAEs at the time of discontinuation will be followed (up to a maximum of 30 days after the last dose of study medication) to a satisfactory resolution, or until it becomes stable, or until it can be explained by another known causes (i.e., concurrent condition or medication) and clinical judgment indicates that further evaluation is not warranted. All ongoing AEs at the time of discontinuation will be followed for up to 7 days. All findings relevant to the final outcome of an AE must be reported in the subject's medical record and recorded on the eCRF page.

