8.1.2. Deaths and Serious Adverse Events

Any deaths that occur during the study will be listed.

Statistical Analysis Plan,
Sponsor Noven Pharmaceuticals, Inc.
Protocol Number HP-5000-US-05
[REDACTED]

Serious adverse events will be listed and also tabulated by system organ class and preferred term and presented by treatment.

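### The SAE definition lets an unplanned admission to work up a new adverse event be classed as non-serious unless another seriousness criterion is invoked

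*Protocol*

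**What the plan says.** Protocol 11.1.3 lists the events that count as serious. One criterion reads "Requires inpatient hospitalization or prolongation of existing hospitalization". The NOTE attached to it removes two kinds of admission. The first is an elective admission for a condition present before exposure to the test drug. The second follows directly: "or a hospital admission for a diagnostic evaluation of an AE, does NOT qualify the condition or event as an SAE". The other two protocol versions in the file carry the same NOTE, and the SAP does not redefine an SAE. Section 11.2.2.2 tells the investigator to judge seriousness by 11.1.3.

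The same section keeps other routes to seriousness. The life-threatening criterion "refers to an event in which the subject was at risk of death at the time of the event". An important medical event is one that "may jeopardize the subject or may require intervention to prevent one of the other outcomes listed in the definition above", and this is left to medical and scientific judgment. Protocol 9.5 adds that an AE leading to an emergency unblinding is handled as an SAE.

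Several rules turn on the classification. SAEs go to the sponsor's designee within 24 hours (11.2.6.1). Non-serious AEs are entered in the eCRF and passed on to the sponsor, with no stated deadline (11.2.6.2). On follow-up of non-serious events, 11.2.5 says: "All ongoing AEs at the time of discontinuation will be followed for up to 7 days". In the report, "Serious adverse events will be listed and also tabulated by system organ class and preferred term and presented by treatment" (SAP 8.1.2).

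**The concern.** The NOTE cuts into the criterion it annotates. Exempting a planned admission for an old condition is coherent, because nothing new has happened to the subject. An admission to evaluate an AE is different, because the AE is by definition a new or worsened on-study event and is the reason for the admission.

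The protocol itself treats gastrointestinal harm as relevant to this drug. The background section names ulcers and lesions among the systemic effects of oral diclofenac, and the exclusion criteria rule out "any GI bleeding (except hemorrhoidal) within 6 months prior to Screening Visit". An event of that kind could plausibly present as an undiagnosed symptom that leads to admission for work-up. A site following the NOTE could then record a non-serious AE, while another site could call the same admission an important medical event.

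What is at stake is prompt notice and consistent classification of a few potentially important events. The trial has about 300 subjects, no data safety monitoring board (Protocol 12) and no planned interim analysis (Protocol 13.4.6), so expedited SAE reports are an important prompt channel.

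**Working it through.** No arithmetic applies. The check sets the passages side by side.

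1. **Scope of the exemption.** In the 11.1.3 NOTE, the words limiting the exemption to elective admission and to a condition predating exposure belong to the first limb. The diagnostic limb has no limit on planning, on when the event began or on the suspected diagnosis. Taken literally, it covers an unplanned admission for a new event.

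2. **What the exemption removes.** It removes the admission as a ground for seriousness. It leaves the other criteria in 11.1.3 and the unblinding route in 9.5 untouched.

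3. **How well the other routes fill the gap.** Death, immediate risk of death and lasting disability are clear but narrow. The natural fallback is the important medical event. That criterion rests on judgment, and it is introduced for situations that may not lead to death or hospitalization. Its illustration is outpatient care: "Examples of such events are intensive treatment in an emergency room or at home for allergic bronchospasm". It therefore seems to assume that admitted subjects are already captured by the hospitalization criterion, which is the assumption the NOTE breaks. The result is uneven: intensive emergency-room treatment without admission can be serious, while an inpatient stay for work-up is excluded as a ground. Unblinding will rarely help, since 11.2.4 says it is unnecessary in most circumstances even after an SAE.

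4. **Consistency with other text.** Protocol 11.2.3 asks sites to document seriousness and gives hospitalization as an example, with no exemption.

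5. **What changes with the classification.**

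| Rule | Classed as SAE | Classed as non-serious AE |
|---|---|---|
| Reporting | Within 24 hours of awareness (Protocol 11.2.6.1) | eCRF entry and onward report, no stated deadline (11.2.6.2) |
| Follow-up if ongoing at discontinuation | Up to 30 days after the last dose (11.2.5) | Up to 7 days (11.2.5) |
| SAE table and listing | Included (SAP 8.1.2, Table 14.3.1.5, Listing 16.2.7.2) | Not included |
| General AE tables and listing | Included | Included (SAP 8.1, Table 14.3.1.2, Listing 16.2.7.1) |

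6. **Limits on the follow-up row.** The 7-day rule concerns only AEs still ongoing at discontinuation. Protocol 11.2 separately says that subjects who complete or stop early are monitored for AEs for 30 days after treatment. The two passages do not fit together and need reconciling.

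7. **Number of events.** This would need the rate of admission for new events and the share admitted for evaluation. The documents give neither.

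**The case against.** A reader might infer that a subject admitted with a suspected serious NSAID event escapes SAE handling altogether. The documents do not support that. The NOTE removes one ground only. A suspected bleed or cardiac event is a natural candidate for the important-medical-event criterion, and may be life-threatening. If the work-up turns into inpatient treatment, the admission is arguably no longer for evaluation alone, although the text does not say so. On this view, what is left is mainly admissions that find nothing serious. The correction stands as far as it goes, but it makes the classification depend on judgment and on how each site reads the NOTE.

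A reader might also infer that SAE reports are the only real-time safety signal. That is too strong. Non-serious AEs reach the sponsor through the eCRF, monitors inspect eCRFs at regular intervals (Protocol 14.4.1), and withdrawals due to AEs require narratives (8.2.3). None of these carries the 24-hour deadline.

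Nor is the event lost from the report. It stays in the AE tables, and Listing 16.2.7.1 has a hospitalization column, though the shell does not say whether that column is completed for an event classed as non-serious.

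Finally, bias between arms is not shown. Sites are blinded, so uneven reading of the NOTE is not tied to treatment, and safety is summarized descriptively.

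**Conclusion.** The conflict between the hospitalization criterion and its NOTE is real and in current text. Following the NOTE can cost an admitted subject's event its 24-hour report and its place in the SAE table and listing, unless another criterion is applied or the blind is broken in an emergency. If the event is ongoing at discontinuation, 11.2.5 also gives it the shorter follow-up.

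It would go too far to say that follow-up of such events generally drops from 30 days to 7, given the 30-day monitoring in Protocol 11.2, or to put a count on misclassified events. The primary endpoint and its analysis are unaffected.

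The conclusion rests on a literal reading of the diagnostic limb. The special-interest section (Protocol 11.2.7) is heavily redacted and the SAE form is not in the file, so nothing is inferred from the absence of another reporting route there. The point is a cheap improvement.

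**What to change.** In the 11.1.3 NOTE, delete the limb on admission for diagnostic evaluation of an AE. Keep the exemption only for elective admission for a condition present before exposure, and state that all other seriousness criteria still apply. Any inpatient admission prompted by a new or worsened event then meets the hospitalization criterion, whatever the work-up shows. Align any SAE form guidance with the amended text. In the same amendment, reconcile the 7-day follow-up in 11.2.5 with the 30-day AE monitoring in 11.2.

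The cost is one deleted clause, one added sentence and the reconciled follow-up wording, with matching form guidance. The downside is a few extra SAE reports for admissions that prove benign.

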11.2. Management of Adverse Events

Adverse events will be collected from the time of first dose administration through the Follow-up Visit or Early Termination Visit, whichever occurs first.

Subjects who complete the Double-blind Treatment Phase or terminate early will continue to be monitored for AEs for 30 days from last day for study treatment, unless they withdraw consent or are lost to follow-up.

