11.2.2.1 Severity of Adverse Events

The clinical severity of an AE will be classified as

Mild	Usually transient and may require only minimal treatment or therapeutic intervention. The event does not generally interfere with usual activities of daily living.
Moderate	Usually alleviated with additional specific therapeutic intervention. The event

	interferes with usual activities of daily living, causing discomfort but poses no significant or permanent risk of harm to the subject.
Severe	Interrupts usual activities of daily living, or significantly affects clinical status, or may require intensive therapeutic intervention.

It is important to distinguish between severe AEs and SAEs. Severity is a classification of intensity whereas an SAE is an AE that meets serious criteria, as described in [Section 11.1.3](#).

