- d. Rescue medication may be used during the Washout Period except within 2 calendar days prior to Visit 2 and within 1 day prior to each subsequent visit.
- e. A standard 12-lead electrocardiogram (ECG) will be performed after the subject has been supine for at least 5 minutes.
- f. Clinical laboratory testing includes hematology, biochemistry, and urinalysis. Results from laboratory testing done at Screening Visit will be used for confirmation of subject eligibility at Baseline Visit.
- g. Fasting glucose and lipids should be performed after 8 to 10 hours of fasting. Subject must be instructed to fast for 8 to 10 hours (no food or drink, except for water) before coming for the Baseline assessments, if not done at Screening.
- h. Subjects will be instructed on how to use of the electronic diary (eDiary) at the Screening Visit. For each 28-day administration period, subjects will be asked to record their NRS score, their intake/use of study drug and rescue medication in the eDiary.
- i. Study treatment will be applied on Day 1 of the Double-blind Treatment Phase. Instructions for application and removal of study drug patches will be provided to the subject at the Baseline Visit (V2).
- j. Dermal evaluations will assess skin adhesion, irritation, discomfort, and adhesive residue.
- k. Screening/Washout Period should be up to 28 days. Washout Period can be initiated 3 days after Screening Visit.

- l. During the Double-blind Treatment Phase, subjects will report the incidence of patch detachment by answering Yes or No and will perform dermal assessments daily at home.
- m. AEs will be collected starting from the first administered dose.
- n. Historical X-rays done within one year prior to the Screening Visit are acceptable. If subject does NOT have any X-Ray done within the past year, a mandatory new X-Ray to confirm the disease will have to be performed prior to starting the Washout Period.
- o. Only for rescue medication.

Note: [REDACTED] should be administered at the Screening and Baseline Visits after the subject has been consented and passed all the eligibility criteria defined in the protocol first.

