3. If the start date is missing but the stop date is not missing and is on or before the day of study drug administration and after the date of signed informed consent, then the AE (or medication) is considered to be before treatment (or prior).

If the start date is not missing but the stop date is missing, then the most conservative approach is taken and medication is considered to be concomitant while the AE is defined by start date.

A treatment related AE is any AE with a relationship to the study drug of “Possibly Related” or “Definitely Related”. Any AE with a missing relationship will be analyzed as treatment related. If an AE has a missing severity, it will be imputed as “Severe”.

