8.1. Adverse Events

All adverse events collected are treatment-emergent adverse events (TEAEs) since only AEs after treatment start are collected. All AEs, and SAEs will be coded using the MedDRA version 19.0 thesaurus.

The frequency and percentage of subjects reporting AEs, grouped by MedDRA system organ class and preferred term, will be tabulated by severity and treatment group for the SAF. Such summaries will be displayed for AEs, SAEs, AEs by relationship to study drug, and AEs by severity.

In the case of multiple occurrences of the same AE within the same subject, each subject will only be counted once for each preferred term. In the summaries showing severity and relationship to study medication the event with the maximum severity or strongest relationship will be reported. If a particular event is missing the severity and/or relationship, then the strongest possible severity or relationship will be assumed for analysis (severity = severe, relationship = definitely related).

Missing and partially missing AE start and/or stop dates will be imputed for the purpose of statistical analysis, according to the specifications described in Section [5.1.8](#).

In the AE data listings, all AEs will be displayed.

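### Serious events in the protocol-required washout have no stated reporting route: AE collection starts at the first patch and no earlier start is given for SAEs

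*Protocol*

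**What the plan says.** The current protocol gives the start of collection in three places.

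- Section 11.2: "Adverse events will be collected from the time of first dose administration".
- Section 11.1.1: "All AEs, regardless of relationship to study drug or procedure, should be collected beginning from after the start of the study drug". It adds that "AEs reported during treatment-free periods before study drug has been administered are not considered AEs" and that "these events are captured on the eCRF as updates to the subject's medical history".
- Schedule of Events (Section 17.1), footnote m: "AEs will be collected starting from the first administered dose". The first patch is on Day 1, the day after randomisation at Baseline (Day 0).

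For serious events, Section 11.2.2.1 says "an SAE is an AE that meets serious criteria". Section 11.2.6.1 requires a report within 24 hours of awareness. It sets when SAE collection ends (the Termination Visit or 30 days after stopping study drug, whichever is longer) but not when it begins.

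Before the first patch, Section 9.10 has subjects stop all prescription and over-the-counter analgesics for 7 to 14 days, or five half-lives if longer, with rescue acetaminophen supplied by the sponsor. Section 10 counts stopping prohibited therapy among the study-related procedures that need prior consent.

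The SAP speaks in two ways. Section 8.1 treats every collected AE as treatment-emergent "since only AEs after treatment start are collected". Section 5.1.7 has rules for AEs or medications with missing dates. One branch classes an event as before treatment when its start date is missing and its stop date "is on or before the day of study drug administration and after the date of signed informed consent".

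**The concern.** The protocol calls the time before the first patch treatment-free, but the trial is already acting on the subject then: it takes away the usual analgesic and hands out another drug. Screening and Baseline blood draws also fall before the first patch, and Section 5.3 names venipuncture as a risk of taking part.

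If a serious event in that period is not an AE, it is not an SAE under Section 11.2.2.1, and nothing in Section 11.2.6.1 clearly requires the 24-hour report. What is at stake is whether the sponsor hears promptly of serious harm during a procedure that the protocol requires. There is no data safety monitoring board (Section 12). The gap concerns subject safety and completeness of reporting; it does not touch the efficacy analysis.

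**Working it through.** **1. The plan's own duration.** Section 10.1.6 gives up to 28 days of screening and washout, 4 weeks of treatment and 1 week of follow-up: 28 + 28 + 7 = 63 days = 9.0 weeks, which matches the stated total. The period before AE collection is therefore up to 28/63 = 44% of participation. By the Schedule (Screening Day -28 to -14, first patch Day 1) it is 15 to 29 days per subject, counting Day 0.

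**2. The part that is intervention.** Section 10.1.6 places the washout in the last 7 to 14 days of screening. For 300 randomised subjects:

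- 300 x 7 / 365.25 = 5.7 subject-years
- 300 x 14 / 365.25 = 11.5 subject-years

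Screen failures who start the washout add to this; their number is not given. The five-half-lives clause can lengthen the washout. Section 7.1 and the Schedule also show it starting at Day -25, against a 14-day maximum elsewhere; those passages must be reconciled. I use 7 to 14 days.

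**3. Chance of at least one event (assumption).** The documents give no pre-dose SAE rate. With a per-subject risk p over the pre-dose period and 300 subjects, the chance of at least one is 1 - (1 - p)^300:

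| Assumed p | Chance of at least one |
|---|---|
| 0.1% | 26% |
| 0.25% | 53% |
| 0.5% | 78% |
| 1% | 95% |

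This shows only that such an event is not far-fetched. It says nothing about cause.

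**4. The SAE route, read across sections.** Section 11.1.1: a pre-dose event is not an AE. Section 11.2.2.1: an SAE is an AE meeting serious criteria. Section 11.2.6.1: no earlier start for SAEs. Together these leave a washout hospitalisation outside the reporting rule. This is an inference from three sections; no single sentence says it.

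**5. Where it would appear.** SAP Section 13.2 puts the medical-history listing (16.2.4.2) and the AE, SAE and death listings (16.2.7.1 to 16.2.7.4) on the safety set, which requires at least one patch. A subject harmed in the washout and never patched is in none of them.

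**6. The inconsistencies.**

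- The Schedule ticks Adverse Events at Baseline (Day 0), but footnote m starts them with the first dose (Day 1). The Baseline procedure list in Section 10.1.2 has no AE review.
- SAP 5.1.7 can class an AE as before treatment; SAP 8.1 says no such AE is collected.
- Under SAP 5.1.7, an AE start date with unknown month, in the year of randomisation, is set to the randomisation date. That is Day 0, one day before the first patch. SAP 8.1 would count the event as treatment-emergent; its imputed date says otherwise. When only the day is unknown, the rule uses the first-dose day instead, so the two imputations do not agree.

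**The case against.** The best case for the plan has several parts.

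- **The SAE gap is an ambiguity.** Section 11.1.3 defines an SAE as any untoward medical occurrence meeting the criteria, Section 11.2.6.1 asks for all SAEs whatever their relationship to treatment, and Section 15.3 requires prompt notice to the IRB of new safety information. This stands in part. A reader might infer that serious harm in the washout would never reach the sponsor; the documents do not show that. They do leave the timed report without a stated start, and notice to the IRB is not an SAE report to the sponsor.
- **The pre-dose period is mostly not intervention.** This stands. A reader might take the full 28 days, 300 x 28 / 365.25 = 23.0 subject-years, as intervention time. The usual washout is 7 to 14 days of it.
- **Events are still recorded.** This stands. A reader might infer that a screen failure leaves no safety record. Section 11.1.1 puts the event on the eCRF, and Section 14.3.2 requires eCRFs and source documents for everyone who signs consent. What is missing is an AE record and a planned AE or medical-history listing.
- **The treatment comparison is not harmed.** This largely stands. The medical-history listing holds dates and ongoing status, Section 11.1.1 makes worsening on treatment an AE, and events before randomisation cannot systematically favour an arm.
- **The SAP conflict is leftover wording.** This stands as to weight. The 5.1.7 branch is a missing-date fallback shared with medications, which do need it. It is still inconsistent with 8.1 and should be aligned.

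Starting non-serious AE collection at the first patch is a defensible choice, and this point does not dispute it.

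**Conclusion.** The point holds in a limited form. AE collection starts at the first patch, no start is given for SAEs, and the protocol's own definitions leave a serious event during the required washout without a stated expedited route to the sponsor. For subjects never patched, it is also absent from every planned AE and medical-history listing. The exposure concerned is about 5.7 to 11.5 subject-years for 300 randomised subjects, plus screen failures. That assumes a 7- to 14-day washout and is not an estimate of harm, since the documents give no event rate. The Schedule and SAP inconsistencies are real but minor. No sample size, power or efficacy result changes. The reason to act is that a reporting gap affecting subject safety can be closed at little cost.

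**What to change.** **Protocol.** Amend Sections 11.1.1, 11.2 and 11.2.6.1 and footnote m so that SAEs are collected from signed consent and reported through the existing SAE route. Keep non-serious AEs from the first patch. Reconcile the Baseline tick in the Schedule, and the same tick in SAP Table 1, with the footnote.

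Do not widen this to every AE attributed to analgesic withdrawal. Section 7.1 requires a baseline pain mean of at least 5, or a rise of at least 2, depending on the starting score. A wider rule could make the required worsening reportable in essentially every randomised subject.

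**SAP.** In Section 8.1, define treatment-emergent by onset on or after the first patch, in line with Protocol Section 13.4.4.1. List pre-treatment SAEs separately for all consented subjects, not the safety set, and keep them out of the treatment-emergent tables. State the population as consented, because the SAP does not define its all-enrolled population. Align Section 5.1.7 with this, including the imputation of a partial AE start date to Day 0. Section 8.1 also cites Section 5.1.8 for date imputation; the rules are in 5.1.7.

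**Cost.** Wording changes in both documents, a small number of extra SAE forms during screening, and one extra listing.
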